9. STATISTICAL DESIGN

[figure not shown]
[figure not shown]
Plasma and CSF samples were selected from healthy control individuals in order to ensure that two age-homogeneous groups were selected, based on the general age distribution of the ALS patient cohort (Control: 55 ± 12.47 years; ALS: 56.58 ± 13.46 years at time of sampling) to negate both age and gender as covariates when analyzing each individual biomarker expression in ALS vs control.

A.

	Control	ALS
Male + Female	n=29	n=31
Age at Sampling (Years)	55.55 ± 12.47	56.68 ± 13.46
Male	21 (72.4%)	21 (67.8%)
Age at Sampling (Years)	55.62 ± 13.44	55.76 ± 13.59
Female	8 (27.6%)	10 (32.2%)
Age at Sampling (Years)	55.38 ± 10.31	58.60 ± 13.69

B.

Welch's t test	
1	Table Analyzed
2	Control_ALS_Age 2
3	Column B
4	ALS
5	vs.
6	Column A
7	Control
8	Unpaired t test with Welch's correction
9	P value
10	0.7379
11	P value summary
12	ns
13	Significantly different (P < 0.05)?
14	No
15	One- or two-tailed P value?
16	Two-tailed
17	Welch-corrected t, df
18	t=0.3362, df=58.00
19	How big is the difference?
20	Mean of column A
21	55.55
22	Mean of column B
23	56.68
24	Difference between means (B - A) ± SEM
25	1.126 ± 3.348
26	95% confidence interval
27	-5.576 to 7.828
28	R squared (eta squared)
29	0.001945
30	F test to compare variances
31	1.164, 30, 28
32	F, DFn, Ddf
33	0.6887
34	P value
35	ns
36	P value summary
37	Significantly different (P < 0.05)?
38	No
39	Data analyzed
40	Sample size, column A
41	29
42	Sample size, column B
43	31

Distribution of ages in across Control and ALS sample cohorts. **A)** Distribution of age at sampling with standard deviation of the total control and ALS patient cohort for this study, as well as breakdown of age at sampling with standard deviation for male and female samples. **B)** Unpaired two-tailed t-test with Welch's correction for age at sampling between control and ALS patient cohorts. No statistically significant differences were identified in age at sampling between groups ($p=0.7379$) or the variance within groups ($p=0.6887$). **C)** Distribution plot of age at sampling for control and ALS patient samples with lines indicating mean group ages. Analyzed by unpaired two-tailed t-test ($p=0.7939$). **D)** Distribution plot of age at sampling for control and ALS patient samples with lines connecting the nearest age match between sample cohorts. Analyzed by paired two-tailed t-test ($p=0.3629$).

All statistical analyses will be performed using GraphPad Prism v.9. Each analyte will be analyzed on an individual analyte-by-analyte basis by unpaired two-tailed t-test, without multiple comparisons performed between analytes as is standard during early-phase exploratory biomarker research.

While several of the proposed biomarkers to be analyzed show strong correlation with age, selecting two age- and gender-homogenous populations for ALS and control samples will mitigate any non-pathological age-related deviations in specific biomarker levels.

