4. OBJECTIVES AND ENDPOINTS

Objectives	Endpoints	Time point(s)
Primary Objectives To validate established ALS-related fluid biomarker levels within the sample cohort.	Primary Endpoint To evaluate levels of established fluid ALS biomarkers such as Nf-L, GFAP, and pTau (T181) in plasma and CSF of ALS patients vs. healthy controls.	Blood and CSF sampling at day 0
Secondary Objectives To identify hypothesis-driven novel fluid biomarkers in ALS related to the IFN-alpha pathway.	Secondary Endpoints To evaluate expression of candidate disease biomarkers in plasma in a cohort of ALS patients. To evaluate expression of candidate disease biomarkers in CSF in a cohort of ALS patients. To compare candidate disease biomarkers specificity and sensitivity with Nf-L, the benchmark biomarker for ALS	Blood and CSF sampling at day 0

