7. STUDY OBJECT

[figure not shown]
PROCEDURE	
Procedure(s)	Biomarker analysis Ulysses Neuroscience Ltd. will perform electrochemiluminescence sandwich ELISA using the Meso-Scale Discovery platform (MESO QuickPlex SQ 120 instrument and analyzed by Discovery Workbench 4.0 software). Samples will be analyzed in parallel using the NULISAseq™ proteomic platform (Alamar Biosciences) for confirmatory analysis of analyte expression using a secondary platform. Data will be analysed as ALS vs healthy control as raw values of each analyte in the samples (pg/mL) and graphed using GraphPad Prism v.9. Specific analytes to be measured include: a) U-Plex Immuno-Oncology Custom: IFN- α 2a, IFN- β , IL-12/IL-23p40, CXCL10/IP10, CCL2/MCP1. b) U-Plex Immuno-Oncology Custom: IFN- γ , IL-6, IL-8, IL-13, TNF- α , CCL5/RANTES. c) R-Plex Human TDP-43: TDP-43. d) S-Plex Neurology Panel 1: GFAP, Neurofilament L, Tau [Total]. e) S-Plex Human Tau: pTau T181 f) S-Plex Human Tau: pTau T217 g) S-Plex Human Tau: pTau T231 h) NULISAseq™ CNS Disease Panel 120 i) NULISAseq™ Inflammation Panel 250 AQ

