Furthermore, sample sizes were established based on Cohen's d power analysis performed based on published meta-analyses of case-control studies reporting effect sizes, or mean or standardised mean difference (SMD) for the benchmark ALS biomarker, Nf-L, in ALS CSF and plasma compared to healthy controls. SMD is statistically equivalent to Cohen's d, in meta-analyses: CSF Nf-L = SMD 1.46, Plasma Nf-L = 1.35 (12). With an effect size (Cohen's d) of 1.06 employed combined with an alpha level of 0.002 (considering all 18 biomarkers) and a minimum power cutoff of 80%, the minimum sample size required to reach statistical power was given to be 30. Considering this power analysis, and that dropout rate is not a factor of consideration for these samples because they have been already collected, and there is no risk of in blood collection, sample volume, or people withdrawing from the study, a sample size of 31 was selected.

	 
Power Analysis performed to inform sample size selection for this study.
 
This study is designed as an exploratory biomarker investigation. Its goals are two-fold: (1) to validate established ALS biomarkers using this cohort, and (2) to assess a broad panel of additional analytes that may be dysregulated in ALS, with a view toward identifying promising candidates for further investigation. We believe that this approach is scientifically justified for an initial exploratory study and aligns with standard practice in early-phase biomarker research. Future studies based on the findings of this work will incorporate expanded cohorts and statistical power analyses derived from this foundational dataset.

Subject Identification	Pseudonymised: participants are identified by a unique coded identification number. This code maintains confidentiality and links the participant to their data without revealing their identity.

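### Section 8 sizes the study at an alpha of 0.002 set for 18 biomarkers, but Section 9 plans unadjusted tests and states no per-test level, so the two sections need to be aligned

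*Combined protocol and SAP*

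**What the plan says.** Section 8 (Sample Size) bases its power calculation on a Cohen's d of 1.06 "combined with an alpha level of 0.002 (considering all 18 biomarkers) and a minimum power cutoff of 80" per cent, and reports that "the minimum sample size required to reach statistical power was given to be 30". The cohort is 29 controls and 31 ALS patients.

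Section 9 (Statistical Design) says that each analyte will be analysed on its own "by unpaired two-tailed t-test, without multiple comparisons performed between analytes as is standard during early-phase exploratory biomarker research". No level is given there for the biomarker tests. The only threshold printed in Section 9 is P < 0.05, in the software output for the comparison of ages between groups.

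The primary endpoint in Section 4 concerns established markers "such as Nf-L, GFAP, and pTau (T181) in plasma and CSF of ALS patients vs. healthy controls", so at least some analytes are tested in two fluids. Section 8 describes a second goal, to assess a broad panel of further analytes "with a view toward identifying promising candidates for further investigation".

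**The concern.** The 0.002 in Section 8 is itself an allowance for testing many markers. Section 9 says that no such allowance is made between analytes. If both statements stand, a reader takes from Section 8 a degree of false-positive control, and a power figure, that the analysis in Section 9 would not have.

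The missing level matters in its own right. Two analysts could follow Section 9 faithfully and describe the same result differently, one reading p-values against 0.05 and the other against 0.002. Nothing in the visible text stops the level from being settled after the data are seen. In a study meant to bring forward candidates, that affects how the results for markers with moderate differences are read.

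**Working it through.** **Inputs.** From Section 8: d = 1.06, alpha = 0.002, power 80%, minimum n = 30, actual groups 29 and 31, and published standardised differences for Nf-L of 1.46 (CSF) and 1.35 (plasma). From Section 9: unpaired two-tailed t-test per analyte. The level 0.05 is an assumption, because Section 9 states none for the biomarkers.

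**1. Reproduce the plan's figure.** Power comes from the non-central t distribution with n1 + n2 − 2 degrees of freedom and non-centrality d × √(n1·n2/(n1 + n2)), assuming equal variances.

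- 30 per group, two-sided 0.002: non-centrality 1.06 × √15 = 4.105, power 80.1%.
- 29 per group: 78.0%. So 30 per group is exactly the minimum.
- 30 in total (15 per group): 33%. The stated 30 must therefore be per group.
- A one-sided t-test would need 27 per group, so the two-sided test is the version that matches.

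**2. Power with the actual 29 and 31 samples.** The non-centrality at d = 1.06 is 1.06 × √(899/60) = 4.103.

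| True d | Two-sided 0.05 | Two-sided 0.002 | Two-sided 0.05/36 = 0.0014 |
|---|---|---|---|
| 0.74 | 80% | 37% | 32% |
| 1.06 | 98% | 80% | 77% |
| 1.35 | 99.9% | 97% | 96% |
| 1.46 | >99.9% | 99% | 99% |

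The effect detectable with 80% power is d = 1.06 at 0.002 and d = 0.74 at 0.05.

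**3. Observed differences on which the two levels disagree.** The observed standardised difference at a given p-value is the critical t on 58 degrees of freedom times √(1/29 + 1/31) = 0.2583.

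- p = 0.05: 2.002 × 0.2583 = 0.52 SD.
- p = 0.002: 3.237 × 0.2583 = 0.84 SD.

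An observed difference between about 0.52 and 0.84 SD has p between 0.05 and 0.002.

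**4. What 18 counts.** Items a to g in Section 7, the MSD assays, list 5 + 6 + 1 + 3 + 1 + 1 + 1 = 18 analytes. That is one fluid; if all are tested in plasma and CSF there are 36 tests. Since 0.05/18 = 0.0028, a level of 0.002 covers 18 tests with a little to spare. It does not quite cover 36, for which 0.05/36 = 0.0014.

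**5. Chance of at least one false positive,** 1 − (1 − alpha)^m, with no true differences and independent tests:

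| Tests (m) | At 0.05 | At 0.002 |
|---|---|---|
| 18 | 1 − 0.95^18 = 60% | 1 − 0.998^18 = 3.5% |
| 36 | 1 − 0.95^36 = 84% | 1 − 0.998^36 = 7.0% |

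The expected numbers of false positives at 0.05 are 18 × 0.05 = 0.9 and 36 × 0.05 = 1.8. Under positive correlation the probabilities in the table are upper bounds. With a common correlation of 0.5 between test statistics, the figures for 36 tests fall to about 55% and 4.5%.

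**The case against.** The strongest reply is that the two sections can be reconciled. The only alpha given for the biomarkers anywhere is 0.002, and a fixed per-test 0.002 is compatible with analyte-by-analyte t-tests and no further multiple-comparison procedure in the software. This stands to the extent that a contradiction is not proven. Section 9 does not say it, however, and 0.002 is already an adjustment for 18 markers, so a plan that describes its tests as unadjusted is more naturally read as not using it.

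It can also be said that the study is openly exploratory, that not adjusting is disclosed, and that Section 8 rests on earlier work and literature as well as on the power calculation. All of that is fair, and unadjusted testing can be acceptable here. It does not explain a sizing alpha that the analysis may not use, or the absence of a level.

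Three stronger readings are tempting but not supported:

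- A reader might infer that the study is too small. It is not: Nf-L at the published effect sizes has at least 97% power at either 0.002 or 0.05.
- A reader might infer that candidates are chosen by a p-value cut-off. No section states such a rule. Section 3 says that promising candidates will be considered alongside clinical data, and Section 4 adds a comparison of sensitivity and specificity with Nf-L.
- A reader might count every target on the two NULISAseq panels as a further uncontrolled test. Section 7 describes that platform as "for confirmatory analysis of analyte expression using a secondary platform", and Section 11 limits the collaborator's work to the scope of this protocol. A large count would require assuming that the panel names are target counts and that all targets are tested separately in both fluids.

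**Conclusion.** The point holds as a mismatch between Sections 8 and 9 together with a missing per-test level. The sample size arithmetic is sound, but it belongs to a two-sided test at 0.002. If testing is unadjusted at an assumed 0.05, the stated 80% power is really 98% at d = 1.06, and the chance of at least one false positive over 18 tests is up to 60% where Section 8 implies 3.5%. Those probabilities assume that no marker truly differs, which is unlikely for a panel that includes established ALS markers. They show the size of the gap between the two readings and do not forecast the result. The consequence is for error control and for how moderate differences are interpreted. The number of samples is unaffected. This should be fixed before analysis, and it does not undermine the benchmark comparison for Nf-L.

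**What to change.** State one two-sided per-test level in Section 9 and make Section 8 agree with it. Either option would do.

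- **(a) Keep unadjusted testing.** State the level in Section 9 (for example 0.05), remove 0.002 from Section 8, and restate power for 29 and 31 samples as 98% at d = 1.06, or 80% at d = 0.74. This is the smaller change. The cost is giving up the family-wise control that 0.002 implies.
- **(b) Carry the sizing alpha into the analysis.** State 0.002 as the per-analyte level in Section 9, reword the phrase about multiple comparisons, and say that the level covers the 18 MSD analytes in one fluid, with 80% power at d = 1.06. To cover both fluids, use 0.05/36 = 0.0014 and restate power as 77%. The cost is lower power for moderate effects: at d = 0.74 it is 37% at 0.002 or 32% at 0.0014, compared with 80% at 0.05.

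Both are changes of wording in Sections 8 and 9 and need no new samples or assays.

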10. DURATION OF THE STUDY, DISCONTINUATION AND WITHDRAWAL

a. Duration of the Study

Duration of enrolment: Plasma and CSF are already available in Biobanking-INSPE

Duration of total study period: 1 year

b. Discontinuation And Withdrawal

Not applicable

11. SAMPLE HANDLING

The samples were taken from each participant (accordingly to routine best clinical practice) as part of a standard clinical investigation and for future research. Upon collection, samples will be immediately processed to preserve their integrity. Blood samples were centrifuged to separate plasma and stored at -80C. CSF was collected in sterile conditions and aliquoted to avoid repeated freeze-thaw cycles that could degrade the samples. All samples were properly labeled with a unique identifier, devoid of any personal identifying information to maintain participant confidentiality. All samples are stored in the iNSPE-Biobank under controlled conditions until analysis.

OSR agrees to provide Ulysses neuroscience with the following biological samples:

- Plasma samples from 31 ALS patients
- CSF samples from 31 ALS patients

The samples are anonymized and do not contain any patient-identifiable information.

The samples are stored and transported under appropriate conditions to ensure their integrity. Shipment shall be carried out through Ulysses Neuroscience Ltd.'s partner company, Biorep, which specializes in the secure transport of biological materials. Biorep shall ensure that all necessary handling and storage conditions are met during transit. Ulysses Neuroscience Ltd. shall be responsible for covering all costs associated with the shipment of the samples. The samples shall be used by Ulysses Neuroscience Ltd. for biomarker research in its own facilities. Ulysses laboratories in Cherrywood (Dublin, Republic of Ireland) are fully equipped for analysis of central and peripheral biomarkers related to neuroinflammation, synaptic plasticity and cytoskeleton integrity. Samples are also to be shared with a collaborator laboratory for further comprehensive protein expression analysis within the scope of the study set out in this protocol. The Ulysses Neuroscience Ltd. team has now collected significant data and performed several studies that clearly underline the importance of biomarkers in psychiatric and rare CNS diseases in bridging preclinical and clinical research.

Ulysses Neuroscience Limited is an Irish CRO providing clinical and preclinical research. It is committed to highest ethical scientific practice for both clinical and preclinical studies. The clinical biomarker studies are ethically reviewed and performed by specialised trained staff.

12. DATA MANAGEMENT

a. Definition of source data and source documents

Clinical Data: Includes all medical history, treatment administration, collected through case report forms (CRFs)

Biomarker Data: Comprises biochemical and other molecular data collected from blood and CSF.

b. Documentation of data in Case Report Forms (CRFs)

All relevant data collected during the study for all the patients enrolled in the study shall be entered in the CRF by the principal investigator or someone authorized by the investigator in a timely manner (as soon as possible after the information is collected) to ensure that they are clear and legible. The physician shall confirm the completeness, correctness, plausibility, and compliance with the ICH guidelines and the institutional SOPs of the data by dated signature. An explanation must be provided for any and all missing data. The entries shall be made with black ballpoint pen.

c. Data Recording and Record Keeping

The Principal Investigator must maintain adequate and accurate records to enable the conduct of the study to be fully documented and the study data to be subsequently verified.

The investigator(s)/institution(s) should permit trial-related monitoring, audits, and regulatory inspection(s), providing direct access to source data/documents.

The investigator must keep the documents on file for at least 25 years after completion or discontinuation of the study. After that period, the documents may be destroyed, subject to local regulations. Before proceeding to documents' destruction, sites must inform the Sponsor Investigator in writing.

d. Data Protection

Data Anonymity and Confidentiality

Anonymity: participants are identified not by name, initials, or birth date but by a unique coded identification number. This code helps maintain confidentiality and links the participant to their data without revealing their identity.

Each investigator assures that patients' anonymity will be maintained and that their identities are protected from unauthorized parties. Particular attention should be paid whenever patient data are supplied to third parties and may be autonomously processed, or biological samples/materials are taken and kept for future research purposes.

The investigator should keep in a confidential way a patient identification log recording both patient code and name. The investigator should also maintain patients' written consent forms, in strict confidence (i.e. not for submission to the Sponsor Investigator).

Authorization and Data Entry

Authorized Personnel: Access to data is restricted to authorized personnel only. This access control is crucial for maintaining the integrity and confidentiality of the data.

13. ETHICAL AND REGULATORY CONSIDERATION

The Principal Investigator ensures that the study is conducted in agreement with this protocol, the Good Clinical Practice, the current version of Declaration of Helsinki and the applicable regulations.

The protocol and any amendments are subject to review and approval by the concerned Ethics Committee(s) and Health Authority(ies)

13.1 Responsibilities of the Investigators

The Investigator(s) undertake(s) the responsibility to perform the study in accordance with this Protocol, Good Clinical Practice, and the applicable regulatory requirements. The Investigator is required to ensure compliance with the investigational product schedule, visits schedule, and procedures required by the protocol. The Investigator agrees to provide all information requested in the Case Report Form (CRF) in an accurate and legible manner. The investigator may implement a deviation from, or a change of, the protocol to eliminate an immediate hazard(s) to study subjects without prior EC approval/favorable opinion. As soon as possible, the implemented deviation or change, the reasons for it, and, if appropriate, the proposed protocol amendment(s) should be submitted. The investigator must have available an adequate number of qualified staff and adequate facilities for the foreseen duration of the study to conduct the study properly and safely.

13.2 Ethics Committee (EC) Approvals

This clinical study protocol as well as the Informed Consent are to be submitted to the appropriate Ethics Committee for only notification or approval, in this case it is mandatory to obtain the written and dated approval, signed by the chairman with Ethics Committee(s) composition. The clinical study the documents reviewed, the list of voting members and their qualifications, and the date of the review should be clearly stated on the written Ethics Committee approval.

14. GENDER MEDICINE IN RESEARCH PROTOCOL

ALS predominantly affects males, with a male/female incidence rate ratio of 1.4, and people in their late adulthood, with median age at diagnosis of 65.2 years for men and 67.0 years for women. To avoid bias in the gender dimension we will implement appropriate protocols for treating male and female biological samples (equal proportion and indistinguishability with respect to gender).

15. QUALITY ASSURANCE AND CONTROL

Quality Assurance and Quality Control systems based on written SOPs are in place at the Sponsor Investigator site.

16. END OF CLINICAL STUDY

In accordance with applicable regulation, ICH GCP and SOPs, the PI shall notify the end of the clinical study within 15 days from the end of the clinical study and the reasons for such action.

17. INTELLECTUAL PROPERTY

A clinical observational study agreement will be stipulated with an ad hoc contract.

18. PUBLICATION POLICY

After completion of the study, the Sponsor Investigator prepares a draft manuscript containing final results of the study on the basis of the statistical analysis. The manuscript is delivered to the co-authors for comments and then sent to a scientific journal for publication.

All publications, abstracts, presentations, manuscripts and slides - issued by the Investigators of the collaborative sites and including data from the present study- should be submitted to and reviewed by the Sponsor Investigator at least 3 (three) weeks in advance the planned date for the submission to the scientific journal.

20. APPENDIX A: AMENDMENT HISTORY

List details of all protocol amendments here whenever a new version of the protocol is produced.

Amendment No.	Protocol Version No.	Date issued	Rationale	Study status	Details of Changes

